**Table 5: Dose Escalation Rules**

Number of Subjects with DLT at a Given Dose Level	Dose Escalation Decision Rule
0 out of 3	Enter 3 subjects at the next higher dose level.
1 out of 3	Will enter at least 3 more subjects at this dose level. If 0 of these additional 3 subjects experience a DLT, will proceed to the next dose level. If 1 or more of this group suffers a DLT, then the dose escalation is stopped, and this dose is declared the MAD. Three (3) additional subjects will be entered at a lower dose level if only 3 subjects were treated previously at that dose.
$\geq 2$	Dose escalation will be stopped. This dose level will be declared the MAD (highest dose administered). Three (3) additional subjects will be entered at a lower dose level if only 3 subjects were treated previously at that dose.
$\leq 1$ out of 6 at highest dose level below the maximally administered dose	This is the MTD. At least 6 subjects must be entered at the recommended dose for the phase 2 recommended dose.

#### 4.1.2.2 Part 2: Dose Expansion Scheme

At least 1 study Investigator and the Sponsor Medical Monitor will meet and decide the dose to be studied in Part 2 before the initiation of the dose expansion cohort (either the MTD dose or dose lower than MTD). This dose will be the recommended Phase 2 dose (RP2D), and all subjects in the expansion cohort will receive this dose. The RP2D may also be determined based on a biological effect of the study drug as determined by anti-tumor activity and immune activation. The RP2D for dose expansion will be communicated via an administrative dosing letter and enrollment in the expansion phase may begin without a protocol amendment.

Approximately 50 subjects with renal cell carcinoma (RCC) will be enrolled into Part 2. Subjects in the expansion cohort will be treated until tumor progression (treatment may continue if there is clinical benefit), death, unacceptable toxicity, symptomatic deterioration, achievement of maximal response, subject choice, the Investigator's decision to discontinue treatment, the subject withdraws consent, or Nektar Therapeutics decides to terminate the trial.

Note: The sponsor reserves the right to evaluate two doses or two dosing schedules in each expansion cohort if necessary based on the safety profile during the dose escalation portion.

#### 4.1.3 Tumor Assessments

Tumor response assessments for all subjects will occur every 8 weeks ( $\pm 7$  days) (see Section 9.0). Tumor response will be evaluated using Response Evaluation Criteria in Solid Tumors (RECIST) version 1.1. Subjects with progressive disease (PD) but with otherwise stable or improved performance and clinical status may continue to be treated with study drug in the event of a perceived benefit per Investigator (e.g., non-availability of alternate standard of care therapies). Subjects with a partial response (PR) or stable disease (SD) will continue to receive NKTR-214 until achievement of a confirmed complete response (CR), disease progression, or intolerability to therapy. It is at the discretion of the Investigator to continue treating subjects with a confirmed CR.

#### 4.1.4 Post-treatment

Subjects who discontinue NKTR-214 due to reasons other than radiographic disease progression will continue radiologic tumor assessments every 3 months until disease progression per RECIST v1.1 or start of subsequent anti-cancer therapy. Subjects will also be contacted for survival every 3 months until death, withdrawal of consent, study termination by the Sponsor, lost to follow-up, or for a maximum of 3 years after Cycle 1 Day 1.

A schematic of the study design is presented in Section 1.1 and the Schedule of Assessments for the Dose Escalation and Dose Expansion cohorts is in Section 1.2.

## 5.0 SELECTION OF STUDY POPULATION

### 5.1 Inclusion Criteria

#### For Parts 1 and 2

1. Willing and able to provide written informed consent.
2. Histologically confirmed diagnosis of a locally advanced (not amenable to curative therapy such as surgical resection) or metastatic solid tumor.
3. Male or female patients, age 18 years or older at the time of signing the informed consent form (ICF)
4. Life expectancy >12 weeks.
5. Patients must not have received interleukin-2 [IL-2] therapy within 12 months of Cycle 1 Day 1.
6. Eastern Cooperative Oncology Group (ECOG) performance status 0 to 1.
7. Measurable disease per RECIST v1.1
8. Sample of archival tumor tissue and fresh baseline tumor biopsies (fresh baseline biopsy is defined as a biopsy specimen taken within 28 days prior to Cycle 1, Day 1) are required, except if inaccessible with Medical Monitor approval. Subjects must consent to allow acquisition of existing formalin-fixed paraffin-embedded (FFPE) material, either a block or unstained slides for performance of correlative studies.
9. Demonstrated adequate organ function, as defined below, within 14 days of treatment initiation:
  - a. WBC count  $\geq 2000/\mu\text{L}$  (after at least 7 days without growth factor support or transfusion)
  - b. Absolute neutrophil count (ANC)  $\geq 1500/\mu\text{L}$  (after at least 7 days without growth factor support or transfusion)
  - c. Platelet count  $\geq 100 \times 10^3/\mu\text{L}$  (transfusions allowed)
  - d. Hemoglobin  $\geq 9.0 \text{ g/dL}$  (transfusions allowed)
  - e. Serum creatinine  $\leq 2 \text{ mg/dL}$  (or glomerular filtration rate  $\geq 40 \text{ mL/min}$ )

- f. Aspartate aminotransferase (AST) and alanine transaminase (ALT)  $\leq 3X$  upper limit of normal (ULN)
  - g. Total bilirubin within normal limits unless associated with hepatobiliary metastases or Gilbert's syndrome, in that case total bilirubin  $\leq 2x$  ULN
10. On stress echocardiogram, documented left ventricular ejection fraction  $>45\%$  on cardiac stress test within 60 days prior to Cycle 1 Day 1. At the discretion of the Investigator, patients who are unable to perform a stress echocardiogram may instead have a multigated acquisition (MUGA) scan or transthoracic echocardiogram (TTE).
11. Oxygen saturation  $\geq 92\%$  on room air. NSCLC patients may use supplemental oxygen.
12. Clinically significant toxic effect(s) of the most recent prior chemotherapy must be resolved to Grade 1 or less (except alopecia and sensory neuropathy). Immune-related AEs from previous therapy must be resolved to Grade 0 (except for endocrinopathies, or rash, which can be Grade 1). If the subject received major surgery or radiation therapy of  $> 30$  Gy, they must have recovered from the toxicity and/or complications from the intervention.
13. Women of childbearing potential must agree to use highly effective methods of birth control (defined as those, alone or in combination, that result in a low failure rate [i.e.,  $< 1\%$  per year] when used consistently and correctly, such as oral contraceptives, surgical sterilization, an intrauterine device, and/or 2-barrier methods [e.g., condom and cervical barrier such as a diaphragm]). Protections against pregnancy must be continued for at least 3 months after the last dose of study drug. All subjects must agree to use double-barrier contraception during participation in this study and for at least 3 months after the last dose of study drug. This criterion may be waived for male subjects who have had a vasectomy  $> 6$  months before signing ICF.

[Redacted]

■ [Redacted]

■ [Redacted]  
[Redacted]

■ [Redacted]  
[Redacted]

■ [Redacted]  
[Redacted]

- e. Clinically asymptomatic in screening.

**15. For expansion cohort only:**

Renal Cell Carcinoma (RCC)

- a. Histologically confirmed diagnosis of unresectable or metastatic RCC with predominantly clear cell elements
- b. Must have received only 1 prior line of anti-angiogenic therapy.
- c. Must not have received prior immunotherapy with immune-modulators including but not limited to checkpoint inhibitors such as anti-PD-1, anti-PD-L1, anti-CTLA-4 antibody and any other antibody or drug specifically targeting T cell co-stimulation or checkpoint pathways, indoleamine 2,3-dioxygenase pathway inhibitors, cancer vaccines, adoptive cell therapies, and cytokine therapies.

**5.2 Exclusion Criteria**

1. Use of an investigational agent or an investigational device within 28 days before administration of first dose of NKTR-214.
2. Females who are pregnant or breastfeeding.
3. Subjects who have an active autoimmune disease requiring systemic treatment within the past 3 months or a documented history of clinically severe autoimmune disease that requires systemic steroids or immunosuppressive agents. (Exceptions include any subject on 10 mg or less of prednisone or equivalent, subjects with vitiligo, hypothyroidism stable on hormone replacement, Type I diabetes, Graves' disease, Hashimoto's disease, alopecia areata, eczema, or with Medical Monitor approval.)
4. History of organ transplant that requires use of immune suppressive agents.
5. Use of warfarin within 14 days of initiating NKTR-214. (Note: Low molecular weight heparin is allowed on the study).
6. Evidence of clinically significant interstitial lung disease or active, noninfectious pneumonitis.
7. Active central nervous system (CNS) metastases.

8. Prior surgery or radiotherapy within 14 days of therapy. Subjects must have recovered from all radiation-related toxicities, not required corticosteroids and have not had radiation pneumonitis.
9. Subjects who have had < 28 days since the last chemotherapy, immunotherapy, biological therapy, or < 14 days from approved tyrosine kinase inhibitor (TKI) therapy (sunitinib, sorafenib, vemurafenib, dabrafenib, cobimetinib), or systemic or inhaled steroid therapy at doses greater than 10mg of prednisone or equivalent before administration of the first dose of study medication.
10. Active infection requiring systemic therapy.
11. Has known hepatitis B virus (HBV) infection (e.g. HBsAg reactive) or hepatitis C virus (HCV) e.g., HCV RNA qualitative is detected).
12. Has known immunodeficiency or active human immunodeficiency virus (HIV 1/2 antibodies).
13. Prolonged QTcF >450 milliseconds (ms) for men and >470 ms for women at Screening
14. History of unstable or deteriorating cardiac disease within the previous 6 months prior to screening including but not limited to the following:
  - a. Unstable angina or myocardial infarction
  - b. Congestive heart failure (New York Heart Association [NYHA] Class III or IV)
  - c. Uncontrolled clinically significant arrhythmias
15. Need for > 2 antihypertensive medications for management of hypertension.
16. Known current drug or alcohol abuse.
17. Any condition including medical, emotional, psychiatric, or logistical that, in the opinion of the Investigator, would preclude the subject from adhering to the protocol.

### **5.3 Removal of Subjects from Study Therapy or Assessment**

Subjects may choose to discontinue the trial at any time, for any reason, and without prejudice to further treatment.

Subjects may stop participating in or be withdrawn from the study for any of the following reasons, but are to be followed according to the procedures section for progression of disease and for safety until resolution or permanent sequelae of all toxicities attributable to the study drug.

- Subject has progressive disease,
- Occurrence of a clinically significant AE found to be unacceptable by the Investigator;
- Subjects who need more than 6 weeks to recover from treatment-related toxicities;
- Symptomatic deterioration,
- Achievement of maximal response,
- Noncompliance of the subject with protocol-mandated procedures based on agreement of both the Investigator and Sponsor;
- Continued participation is no longer in the subject's best interest in the opinion of the Investigator;
- If a female subject becomes pregnant, administration of the study drug must be discontinued immediately;
- Withdrawal of Consent;
- The study is terminated by the Sponsor.

In the event of a subject's withdrawal, the Investigator will promptly notify the Sponsor and make every effort to complete the Early Termination assessments specified in the Schedule of Assessments (Section 1.2).

## **6.0 TREATMENT PLAN (DOSE ESCALATION AND DOSE EXPANSION)**

### **6.1 Overview**

The study has a screening period, treatment period and post-treatment period. All procedures are outlined in the Schedule of Assessments (Section 1.2).

### **6.2 Screening Period**

Subjects will provide written informed consent to participate in the study before completing any protocol-specified procedures or evaluations not considered to part of the subject's normal care. After signing the ICF subjects will be evaluated for entry criteria during the Screening period within 28 days before administration of study drug.

### **6.3 Treatment Period**

Subjects who meet the selection criteria may start NKTR-214 treatment within 28 days following the Screening visit. The treatment period of the study is divided into multiple 21-day cycles with associated evaluations and procedures. Results of the assessments must be reviewed and documented before administering the first dose of the next cycle. No subject will be permitted escalation of dose level after assignment to a specific NKTR-214 dose level. Dose reductions after Cycle 1 due to AEs may occur following a discussion with the site Investigator and Medical Monitor. Every effort should be made to schedule visits within the protocol-specified windows.

For each dose level in Part 1, the first subject enrolled into a given dose cohort will be treated and monitored from Cycle 1, Day 1 through Cycle 1, Day 5 for safety and tolerability prior to dosing of additional subjects at that dose level.

Cycle 1, Day 1 will be the first day of treatment with NKTR-214 and Cycle 2, Day 1 will be the first day of the second dose of NKTR-214. Results from Day 1 laboratory evaluations must meet eligibility criteria prior to Cycle 1, Day 1 dosing.

During dose escalation, subjects who drop out prior to completion of Cycle 1 will be replaced unless the subject discontinued due to a DLT. During dose expansion, subjects will not be replaced.

Subjects will be treated until unacceptable toxicity, or disease progression per RECIST version 1.1. In the presence of disease progression, treatment may continue if there is clinical benefit as determined by the Investigator based on a reduction of symptoms related to cancer and absence of clinical deterioration or decline in ECOG performance status.

Note: Dosing may change to q14d or q28d following review and agreement by the Sponsor and Investigators. The change in cycle length will be determined by review of safety data and PK review of study drug.

After completing the pre-dosing procedures, administer NKTR-214 as an IV infusion over  $15 \pm 5$  minutes (Section 6.11).

Postdosing:

- The study site must be equipped for medical emergencies and have access to an intensive care unit.
- During dosing days, subject will stay in clinic for observation approximately 1 hour after dosing.
- Administer at least 2 liters of fluid (IV or self-administered orally [e.g., fluid containing electrolytes]) during Days 1 to 5 of every cycle.
- Advise subjects to restrain from strenuous activity and avoid long hot showers and saunas for Days 1 to 5 of every cycle (Parts 1 and 2, dose escalation and expansion).
- Should a subject experience hypotension at any time during a cycle, IV fluid administration has been effective. Subjects with adrenal insufficiency requiring corticosteroid supplementation may benefit from additional short term corticosteroid use of up to 5mg/day of prednisone for the management of hypotension. Vasopressors may also be used for hypotension.
- A Patient Wallet Card is available that contains important safety information.

### Vital Signs

Vital signs (temperature, pulse, respiration, systolic and diastolic blood pressure, and oxygen saturation), concomitant medications, and potential AEs will be assessed either at the study site or as a Home Health visit as needed. Qualified home health personnel may visit the subject to take vital sign measurements. The results of these measurements will be provided to the Investigator or designee. The Investigator will be responsible for assessing any adverse events and for following up with the subject.

### 6.4 Radiographic Assessments

Radiographic assessments (chest/abdomen/pelvis) by computed tomography (CT) scan or magnetic resonance imaging (MRI) are required for all subjects for tumor measurements. CT

scans or MRIs will be performed, target lesions measured, and tumor response evaluation completed at Screening (within 28 days prior to Cycle 1 Day 1) and every 8 weeks ( $\pm 7$  days) from Cycle 1 Day 1 while on study treatment, until PD is noted (even if subject has stopped treatment with study drug) or the subject withdraws consent.

The same method of assessment (CT or MRI) and the same technique for acquisition of images must be used for all study assessments. Baseline imaging should be done at the same institution/facility which will be used to measure response during the subject's participation in the study. Radiographic assessments will also be conducted by an independent central imaging core laboratory for all dose escalation and dose expansion cohorts. There must at least one measurable solid tumor by RECIST version 1.1 present on the Screening scan.

### **6.5 Post-treatment Period**

The EOT/Early Termination visit is to occur within 30 days (+ 10 days) after last dose of study drug.

Subjects who reach the EOT visit without radiographic disease progression must continue to undergo immunogenicity testing and radiological assessment at the interval of every 3 months ( $\pm 7$  days) until either disease progression per RECIST version 1.1 or the start of a new anti-cancer therapy. Subjects will also be followed every 3 months ( $\pm 7$  days) for survival until death, lost to follow-up, study termination by Sponsor, or 3 years have passed since the subject's first dose.

For any toxicity the Investigator attributed to study drug, the Investigator will assess the subject to determine whether the toxicity resolved or worsened. Information on whether the toxicity resolved or worsened must be entered into the eCRF.

### **6.6 Pharmacokinetic Measurements**

Blood samples for pharmacokinetic analysis will be collected and processed as outlined in a Laboratory Manual that will be provided to the site. Briefly, at each designated sampling time, using Sponsor-provided kits, collect 2 mL or 4 mL whole blood into tubes; centrifuge to obtain plasma. Aliquot plasma in plasma storage tubes, freeze, and ship as outlined in the Laboratory Manual.

For all PK blood samples, the date and actual time collected must be recorded. For subjects whose only peripheral access is via a venous access device or peripherally inserted central catheter, refer to the Laboratory Manual for the proper technique to ensure undiluted whole blood for PK assessments.

## 6.7 Immunogenicity Measurements

Serum samples will be collected and processed as outlined in the Laboratory Manual that will be provided to the site. Briefly, at each designated time point, collect 5-10 mL of blood into serum collection tube, harvest serum, freeze, and ship as outlined in the Laboratory Manual.

## 6.8 Biomarker Measurements

Blood and tumor tissue biopsies will be collected and processed as outlined in the Laboratory Manual that will be provided to the site. Briefly, for blood biopsies, at each designated time point, collect 4x10 mL of blood into green-topped blood collection tubes and 1x10 mL of blood into red-topped blood collection tubes. For optional blood biopsies at time of optional tumor biopsies, collect 1x10 mL of blood into green-topped blood collection tube. For tumor biopsies, collect core biopsies or biopsies with a volume  $\geq 100 \text{ mm}^3$ , and divide into 3 portions. One portion will be FFPE for immunohistochemistry (IHC) analysis, one portion will be used for RNA isolation and molecular characterization, and one portion will be used to analyze TILs using flow cytometry. Refer to the Laboratory Manual for specific instructions on sample processing, storage, and shipping.

### 6.8.1 Biomarker Blood Collection Times and Assessments

Blood for biomarker analysis will be collected as described in the Schedule of Assessments (Section 1.2). The whole blood correlative pharmacodynamic samples will be analyzed by flow cytometry for changes in markers of immune cell populations, including, but not limited to, markers for immune cell populations (T lymphocytes, B lymphocytes, natural killer cells, monocytes, memory T cell subsets, Tregs, and T-cell activation). In addition, whole blood samples will be obtained for evaluation in assays of immune function such as stimulated cell activation (assessed by marker expression, cytokine secretion, proliferation, etc.), isolation of peripheral blood mononuclear cells to assess immunodiversity, and miRNA/mRNA analysis, and genetic profiling.

### 6.8.2 Tumor Tissue Biopsy Collection Times and Assessments

Archival tumor samples and fresh tumor biopsies (defined as a biopsy specimen taken within 28 days prior to the first dose of study treatment) will be required at baseline. For archival unstained tumor samples, a minimum of 10 slides must be submitted (no more than 30 days after first dose). Exceptions may be made with Medical Monitor approval in cases where fresh tumor tissue and/or archival tumor samples are inaccessible. A biopsy specimen from a sample taken since completion of the most recent prior systemic treatment may be acceptable in lieu of a fresh biopsy with medical monitor approval. Tumor biopsy collection is described in the Schedule of Assessments (Section 1.2). Exceptions will be made with Medical Monitor approval in cases

where tumor tissue is inaccessible. Only 20 tumor biopsies will be collected in Part 2. Biopsies should be performed on lesions that have not been exposed to prior radiation. Tumor lesions used for biopsy should not be lesions used as target lesions, unless there are no other lesions suitable for biopsy. If a target lesion is used for biopsy, the lesion must be  $\geq 2$  cm in the longest diameter. Pre- and post-treatment tumor tissue biopsies should be taken from the same lesion, if feasible. Tumor tissue biopsies will be used for characterization of infiltrating immune cell populations using a panel of markers (including, but not limited to CD3, CD4, CD8, CD25, FoxP3, CD68, CD56, CD20, CD45RO, PD-1, CTLA-4, and granzyme B), using IHC, flow cytometry, mass spectroscopy, or other similar techniques. Biopsy samples may also be used to investigate molecular signatures. DNA and/or RNA may be extracted from these samples to do somatic mutation analysis and gene expression analysis. Genes to be assayed may include, but not be limited by those with known driver mutations in solid tumors. These samples will be analyzed by the sponsor or designee.

### **6.8.3 Stool Sample Collection Times and Assessments**

A stool sample from a single bowel movement will be collected by subjects participating in the expansion phase of the study prior to administration of the first dose. Subjects will be provided with a materials kit and instructions for collecting the stool sample. Stool samples will be processed to extract and sequence microbial DNA and RNA as outlined in a Laboratory Manual.

## **6.9 Determination of Dose-Limiting Toxicities**

Based on the preclinical toxicology data and the anticipated half-life of NKTR-214 (15-20 hours), drug-related toxicity is most likely to occur during treatment or within 10 days following treatment. Based on this, dose-limiting toxicities (DLTs) will be assessed in the first cycle for all subjects enrolled to a specific cohort (same dose level). If DLTs are not observed, dose escalation will be permitted and enrollment will begin at the next successive ascending dose cohort. Intra-subject dose escalation will not be permitted. Dose reduction is allowed in subjects based on toxicity with approval from the Medical Monitor.

Unless otherwise suggested by clinical data, a dose-limiting toxicity (DLT) is defined as a Grade 3 or higher study drug-related or possibly related AE occurring within the first cycle of dosing (excluding Grade 3/4 transient lymphopenia < 14 days in duration, tumor flare defined as local pain, irritation, or rash localized at sites of known or suspected tumor, a transient, reversible  $\leq$  grade 3 infusion AE, non-clinically significant laboratory abnormalities, or fatigue lasting less than 72 hours) using NCI CTCAE version 4.03.

Delayed DLTs are drug-related adverse events that occur after Cycle 1. Delayed DLTs will not be used to determine the MTD for dose escalation. Delayed DLTs will be collected and evaluated by the Investigators and the Sponsor on an ongoing basis.

All drug related adverse events after Cycle 1 will continue to be collected and evaluated by the Investigators and the Sponsor on an ongoing basis and will be taken into consideration in determining the MTD.

All AEs that meet DLT criteria, as well as any  $\geq$  Grade 3 immune-related adverse event (regardless of attribution), must be reported to the Sponsor, within 24 hours using the same rapid notification procedures that are used for serious AEs (Section 8.7).

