
Key Inclusion Criteria:
	
For each dose escalation cohort, the first subject enrolled to the cohort will be treated on Cycle 1 Day 1 and monitored for tolerance through Cycle 1 Day 5 prior to dosing of the additional subjects at that dose level. Safety data from Cycle 1 will be utilized to assess dose escalation for each new cohort.
 
A DLT is defined as a Grade 3 or higher study-drug-related or possibly related adverse event (AE) occurring within the first cycle of dosing (excluding Grade 3/4 transient lymphopenia < 14 days in duration, tumor flare defined as local pain, irritation, or rash localized at sites of known or suspected tumor, a transient, reversible ≤ grade 3 infusion AE (< 24 hours), non-clinically significant laboratory abnormalities, or fatigue lasting less than 72 hours) using National Cancer Institute (NCI) Common Terminology Criteria for AEs (CTCAE) version 4.03.
 
Part 2: Dose Expansion
 
Enrollment into the renal cell carcinoma cohort may commence once the MTD or RP2D has been determined.
 
Subjects in the dose expansion cohort will be treated every 21 days (q21d), every 14 days (q14d), or every 28 days (q28d) until tumor progression (treatment may continue if there is clinical benefit as determined by the Investigator), death, unacceptable toxicity, symptomatic deterioration, achievement of maximal response, subject’s choice, the Investigator’s decision to discontinue treatment, the subject withdraws consent or Nektar Therapeutics decides to terminate the trial.
 
For Parts 1 and 2:
 
 
• Willing and able to provide written informed consent.
 
• Histologically confirmed diagnosis of a locally advanced (not amenable to curative therapy such as surgical resection) or metastatic solid tumor.
 
• Male or female patients, age 18 years or older at the time of signing the informed consent form (ICF).
 
• Life expectancy > 12 weeks.
 
• Patients must not have received interleukin-2 [IL-2] therapy within 12 months of Cycle 1 Day 1.
 
• Eastern Cooperative Oncology Group (ECOG) performance status 0 to 1.
 
• Measurable disease per RECIST version 1.1.
 
 
For Part 2 only:
 
Renal Cell Carcinoma (RCC)
 
 
a. Histologically confirmed diagnosis of unresectable or metastatic RCC with predominantly clear cell elements.
 
b. Must have received only 1 prior line of anti-angiogenic therapy
 
c. Must not have received prior immunotherapy with immune-modulators including but not limited to checkpoint inhibitors such as anti-PD-1, anti-PD-L1, anti-CTLA-4 antibody and any other antibody or drug specifically targeting T cell co-stimulation or checkpoint pathways, indoleamine 2,3-dioxygenase pathway inhibitors, cancer vaccines, adoptive cell therapies, and cytokine therapies.
 
	

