A DLT is defined as a Grade 3 or higher study drug-related or possibly related AE occurring within the first cycle of dosing (excluding Grade 3/4 transient lymphopenia < 14 days in duration, tumor flare defined as local pain, irritation, or rash localized at sites of known or suspected tumor, a transient, reversible  $\leq$  grade 3 infusion AE [ $<$  24 hours], non-clinically significant laboratory abnormalities, or fatigue lasting less than 72 hours) using National Cancer Institute (NCI) Common Terminology Criteria for AEs (CTCAE) version 4.03.

All drug related AEs after Cycle 1 will continue to be collected and evaluated by the Investigators and the Sponsor on an ongoing basis and may be taken into consideration in determining the MTD.

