10.1 Dose Limiting Toxicity

A dose-limiting toxicity (DLT) is defined as a grade 3 or higher related or possibly related AE occurring within the first cycle of dosing except:

- Grade 3/4 transient lymphopenia < 14 days in duration,
- tumor flare defined as local pain, irritation, or rash localized at sites of known or suspected tumor,
- a transient, reversible \leq grade 3 infusion AE,
- non-clinically significant laboratory abnormalities, or
- fatigue lasting less than 72 hours

Delayed DLTs are AEs that meet the definition of DLT events and occur after Cycle 1. DLTs and delayed DLTs will be summarized separately for each dose cohort. All DLTs and delayed DLTs will be listed by subject.

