14 CHANGES TO PROTOCOL-SPECIFIED ANALYSES

No changes from the protocol specified analyses are planned.

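### The DLT definition excuses an infusion AE only if it lasts under 24 hours in the synopsis and protocol 4.1.2.1, but sets no hour limit in protocol 6.9 and SAP 10.1, and this can change a Part 1 escalation decision

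*Protocol*

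**What the plan says.** All four statements of the definition agree on the core: a related or possibly related AE of Grade 3 or higher in Cycle 1, with listed exclusions. They differ on the infusion-event exclusion.

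| Place | Wording at the infusion-event exclusion | Hour limit |
|---|---|---|
| Protocol 1.0 Synopsis | "24 hours), non-clinically significant laboratory abnormalities, or fatigue lasting less than 72 hours" (the first words close a bracketed less-than-24-hour limit) | under 24 hours |
| Protocol 4.1.2.1 | "grade 3 infusion AE [ $<$ 24 hours" | under 24 hours |
| Protocol 6.9 | "grade 3 infusion AE, non-clinically significant laboratory abnormalities, or fatigue lasting less than 72 hours" | none |
| SAP 10.1 | "grade 3 infusion AE" | none |

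Every version requires the event to be transient and reversible. Protocol 6.9 alone begins "Unless otherwise suggested by clinical data, a dose-limiting toxicity (DLT) is defined as".

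Table 5 of the protocol gives the consequence when three subjects are added after 1 DLT in 3: "If 1 or more of this group suffers a DLT, then the dose escalation is stopped, and this dose is declared the MAD". SAP 14 states "No changes from the protocol specified analyses are planned".

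Three neighbouring rules also differ:

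- **Denominator.** Protocol 10.5.2 tabulates DLT incidence on the DLT Population. SAP 10 uses the safety population unless it says otherwise, and SAP 10.1 names no other set.
- **Events after Cycle 1.** Protocol 6.9 defines delayed DLTs as drug-related AEs after Cycle 1 and bars them from the MTD determination for dose escalation. Its next paragraph says drug-related AEs after Cycle 1 will count towards the MTD. Protocol 4.1.2.1 says they may, and SAP 3 says they will. SAP 10.1 defines a delayed DLT more narrowly, as an event that meets the DLT criteria.
- **Replacement.** Protocol 4.1.2.1, 6.3 and 10.3 replace a subject who leaves Cycle 1 unless the reason is a DLT. SAP 3 replaces unless the reason is toxicity of any kind.

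**The concern.** Defining the MTD is a primary objective, and the synopsis makes DLT incidence by dose cohort a primary safety analysis. Both rest on which events count. Protocol 4.1.2.1 and 6.9 both govern Part 1, and SAP 10.1 governs the reporting. An investigator using 6.9, the section headed as the place where DLTs are determined, can classify the same event differently from one using 4.1.2.1. In cohorts of 3 to 6 subjects a single classification can decide between escalating and declaring the MAD. Protocol 6.9 also ties 24-hour expedited reporting to AEs that meet the DLT criteria, so the version used affects reporting as well.

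The denominator and the other rules matter less. They affect the reported rate, who is replaced, and how clearly the basis for the final MTD is stated.

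**Working it through.** **Plan's own figures.** The point disputes none. The nearest figures that depend on the DLT definition are in Tables 7 and 8. Taking the smallest count x for which Pr(rate > 0.30 | beta(0.6 + x, 1.4 + n − x)) > 0.95 reproduces all 74 boundaries in Table 7 (n = 6 to 79). Exact recursion over them gives suspension probabilities of 0.0005, 0.0181, 0.2019, 0.7593, 0.9905 and 1.000. Table 8 states 0.001, 0.018, 0.202, 0.759, 0.991 and 1.000.

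**Does the word transient supply the missing limit?** No. The same list in 6.9 excludes "Grade 3/4 transient lymphopenia < 14 days in duration", so the word can cover many days. A related Grade 3 infusion AE lasting 30 hours and then resolving is a DLT under 4.1.2.1 and can be excused under 6.9.

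**Worked case.** The first 3 subjects have one undisputed DLT. Among the next 3, one has that 30-hour event and no other DLT. Under 4.1.2.1 the count is 2/6: stop and declare the MAD. Under 6.9 it can be 1/6: escalate.

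**Size.** Table 5, applied mechanically with exactly 3 added subjects, escalates with probability

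E(p) = (1 − p)^3 + 3p(1 − p)^2 × (1 − p)^3.

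Let p be the DLT rate under 6.9 and r the share of subjects whose only qualifying event is a Grade 3 infusion AE of 24 hours or more. The rate under 4.1.2.1 is then p + r. The documents do not give r, so 1%, 2% and 5% are assumed, with every such event excused under 6.9. For p = 0.15: E = 0.6141 + 0.45 × 0.4437 = 0.8138. For p + r = 0.20: E = 0.5120 + 0.60 × 0.3277 = 0.7086.

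| p | E(p), 6.9 | E(p + r), r = 1% | r = 2% | r = 5% |
|---|---|---|---|---|
| 0.10 | 90.6% | 88.9% (1.7 lower) | 87.1% (3.5) | 81.4% (9.2) |
| 0.15 | 81.4% | 79.3% (2.0) | 77.3% (4.1) | 70.9% (10.5) |
| 0.30 | 49.4% | 47.4% (2.0) | 45.4% (4.0) | 39.6% (9.8) |

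Differences are in percentage points, from unrounded values. On the listed criteria every 6.9 DLT is also a 4.1.2.1 DLT. A cohort that escalates under 4.1.2.1 therefore also escalates under 6.9, and each difference equals the probability that the two versions give different decisions.

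**Denominator.** Suppose 7 subjects are treated, 1 has a DLT, and one DLT-free subject leaves early and is replaced. On the DLT Population the rate is 1/6 = 16.7% (exact 95% CI 0.4 to 64.1%). On the safety population it is 1/7 = 14.3% (0.4 to 57.9%).

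**Replacement.** A subject who leaves Cycle 1 for a toxicity that is not a DLT is replaced under the protocol. Under SAP 3 the subject is not replaced, yet is also outside the DLT Population.

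**The case against.** The strongest reply is that 4.1.2.1 plainly leads. The synopsis matches it, and protocol 10.2.1 cites it when it needs a DLT definition, so 6.9 looks like an incomplete restatement and not a rival rule. That is probably how the gap arose. But no text ranks the sections, and the SAP repeats the version without the limit.

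It can also be said that the percentages overstate the effect. An investigator may decline to call a day-long Grade 3 event transient after a 15-minute infusion. SAP 3 treats the 3+3 design as a guide, and 4.1.2.1 lets cohorts be enlarged. This stands: the figures are upper bounds for the assumed shares.

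On the secondary items, SAP 7, SAP 14 and protocol 10.5.2 together point to the DLT Population, so SAP 10.1 reads as an omission. For later events there is a coherent reading: Cycle 1 events drive cohort decisions and later events inform the final MTD. It is not stated, and no effect on any figure is shown.

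The documents do not support four stronger readings that a reader might infer:

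- **That 6.9 is always the less cautious version.** This holds on the listed criteria only. The override clause could add a DLT as well as remove one.
- **That Part 2 suspension is compromised.** Protocol 10.2.1 takes its definition from 4.1.2.1.
- **That the DLT Population is defined differently in the two documents.** Protocol 10.4 and SAP 7 use the same words.
- **That this population must be redefined** to catch a subject who has a DLT but leaves Cycle 1 for another recorded reason. Protocol 4.1.2.1 counts a DLT on occurrence, so escalation is unaffected. At an assumed 15% DLT rate with 5% of such subjects leaving, 50 × 0.15 × 0.05 ≈ 0.4 subjects are involved. If subjects with and without a DLT leave equally often, the present population gives 15.0% on average. Redefining it would give 0.15 / (0.15 + 0.85 × 0.95) = 15.7%.

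**Conclusion.** The conflict over the 24-hour limit is real and should be fixed. It is a wording defect in a rule that serves a primary objective, not an objection to the 3+3 design. On the listed criteria it can move a Part 1 decision only towards escalation. At a 15% rate of other DLTs the shift is at most about 2, 4 or 10.5 points for assumed event shares of 1%, 2% or 5%. Those shares are not in the documents, and the bound assumes that every such event is excused and that Table 5 is applied mechanically. The wording conflict itself rests on no assumption.

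The denominator omission in SAP 10.1 also holds, but changes only reported rates. The inconsistencies on later events and on replacement are minor points of clarity.

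**What to change.** **Main change.** Put the 4.1.2.1 definition, with the 24-hour limit, word for word into protocol 6.9 and SAP 10.1. Delete the override clause in 6.9, or state who may apply it and how its use is documented.

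**Secondary changes.**

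- Name the DLT Population in SAP 10.1 as the denominator for Cycle 1 DLT incidence, to match protocol 10.5.2.
- State one rule in protocol 6.9, protocol 4.1.2.1 and SAP 3: cohort escalation uses Cycle 1 DLTs only, and the final MTD/RP2D decision also reviews later drug-related AEs. Use the SAP 10.1 definition of a delayed DLT throughout.
- Use one replacement rule in protocol 4.1.2.1, 6.3, 10.3 and SAP 3.

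**Cost.** These are wording changes in the protocol and SAP, with no change to sample size or design. Restoring the limit makes escalation slightly more cautious than 6.9 as written.
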